 Lymphoma: CT including at least the chest, abdomen and pelvis or PET/CT is required for response (systemic B and T-cell lymphoma patients only) assessment. A bone marrow will only be repeated to confirm a complete response if previously known to be involved. Cutaneous T-cell lymphoma patients will have imaging at baseline and (CTCL) will have an mSWAT (Appendix I) performed monthly for the first three cycles and then at each response assessment timepoints (end of cycle 4, 6 and thereafter at the end of every third cycle). In CTCL patients, imaging will be repeated if appropriate (patients with known nodal or visceral disease) every other cycle. Sezary panel in patients with Sezary syndrome. Cutaneous lymphoma patients without nodal or visceral disease will have imaging repeated only to confirm a complete response. After cycle 12, patients on continuous therapy may be imaged as clinically indicated, at the discretion of the treating physician. At discontinuation of therapy, end of study response assessments – including imaging – should be performed.

Serum/urine protein electrophoresis, serum/urine immunofixation, quantitative immunoglobulins, and serum free light chains are required if appropriate for (multiple myeloma patients only) response assessment. A bone marrow will only be repeated if to confirm a complete response. Patients with non-secretory myeloma will have the bone marrow assessment repeated if they have been otherwise clinically stable (i.e. without new lytic lesions, soft-tissue plasmacytomas or hypercalcemia). A skeletal survey is allowed to rule out bone lesions for evaluation of disease progression and to confirm a complete response in nonsecretory multiple myeloma. PET/CT should be performed at screening and to confirm responses in patients with soft tissue plasmacytomas.

 An additional safety assessment will be done 28 days (+/- 2 days) following the last dose of protocol therapy.

 If romidepsin is omitted on day 8 per dose reduction algorithm (Table 4) then hematologic and electrolyte assessments are not required.

Response assessment will be performed at the end of cycles 2, 4, and 6. Thereafter, response assessment will occur at the end of every third cycle (9,12,15, etc.) until disease progression or removal from study. Myeloma patients will have their disease assessed after each cycle.

 +/- 3 days

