#### **12.1.1 Response Criteria**

Responses are as follows for patients with measurable M protein:

- Stringent Complete Response (sCR) = Undetectability of the M protein by immunofixation of serum and urine, normalization of the serum free light chain ratio, and normalization of the bone marrow biopsy, including  $\leq 5\%$  total plasma cells and lack of clonal excess by kappa/lambda staining.
- Complete Response (CR) = Undetectability of the M protein by immunofixation of serum and urine or normalization of the serum free light chain ratio in patients without a detectable serum or urine M-spike at baseline and normalization of the bone marrow biopsy, including  $<5\%$  total plasma cells and lack of clonal excess by kappa/lambda staining.
- Very Good Partial Response (VGPR) = Serum and urine M component detectable by immunofixation only but not by electrophoresis or a reduction of  $\geq 90\%$  in the M-protein concentration component plus a urine M-component  $<100\text{mg}/24\text{ hours..}$
- Partial Response (PR) = 50% or greater reduction of serum M-protein and reduction in 24-hour urinary M-protein by  $>90\%$  or to  $>200\text{mg}/24\text{ hours.}$  If the serum and urine M-protein are not measurable, a decrease of 50% in the difference between involved and uninvolved FLC levels is required in place of M-protein criteria. In addition to the above criteria, if present at baseline,  $>50\%$  reduction in the size of soft tissue plasmacytomas is also required.
- Minimal Response (MR) = A reduction of  $>25\%$  but  $<50\%$  in the M-protein concentration.
- Stable disease (SD) = An increase in the M protein by  $< 25\%$  from baseline or a decrease in the M protein by  $< 25\%$  from baseline.
- Progressive Disease (PD) = Increase of 25% from lowest response value in any of the following: serum M-component (minimal absolute increase of  $0.5\text{g/dl}$ ), urine M-component (absolute increase must be  $200\text{mg}/24\text{h}$ ), and/or only in patients without measurable serum and urine M-protein levels: the difference between involved and uninvolved FLC levels (absolute increase must be  $10\text{mg/dl}$ ) and/or the occurrence of new hypercalcemia, new lytic lesions by skeletal survey, or new soft tissue plasmacytomas.

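### The plasmacytoma condition for myeloma response is written only into PR, so read literally an unchanged baseline lesion blocks PR but not VGPR, CR or sCR

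*Combined protocol and SAP*

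**What the plan says.** Section 12.1 adopts the IMWG criteria by citation, and Section 12.1.1 then writes out a definition for each category.

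- **PR** is the only response category with a lesion condition. It is introduced by "In addition to the above criteria, if present at baseline", and says that a more than 50% "reduction in the size of soft tissue plasmacytomas is also required".
- **VGPR** rests on the M-component: "Serum and urine M component detectable by immunofixation only but not by electrophoresis or a reduction of" at least 90%, the latter with urine M-component below 100 mg/24 h.
- **CR** needs negative immunofixation, or a normal light-chain ratio "in patients without a detectable serum or urine M-spike at baseline and normalization of the bone marrow biopsy".
- **sCR** needs negative immunofixation plus "normalization of the serum free light chain ratio, and normalization of the bone marrow biopsy, including" a plasma cell limit and no clonal excess.
- **PD** lists "new lytic lesions by skeletal survey, or new soft tissue plasmacytomas", so an unchanged baseline lesion is not progression.

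Footnote 8 of the Table 7 legend adds: "PET/CT should be performed at screening and to confirm responses in patients with soft tissue plasmacytomas". It gives no size or resolution threshold. Section 16.1.2 makes responses subject to review by a central committee, which can call for radiology.

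Section 4.1 counts CR, VGPR and PR in ORR, adds MR for CBr, and starts DOR at the first documented response.

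**The concern.** Response categories should be ordered, so that a patient in a higher one also satisfies the conditions of those below it. Here the lowest category counted in ORR demands something of the lesion that the three above it do not. Two patients with the same unchanged mass could then be classified in opposite ways, one a non-responder and the other a complete responder, on biochemistry and marrow alone.

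ORR, complete response rate, VGPR/PR rate and CBr are stated secondary objectives. A response scored in this way also supplies a TTR and starts a DOR clock while extramedullary disease is unchanged. The phase IIa efficacy data are meant as background for a possible subtype-specific phase II study, so a single patient in a small myeloma cohort is visible in the result.

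**Working it through.** The plan gives no figure on this point, so there is nothing to reproduce. The check applies the written definitions to test records and then sizes one patient.

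**Step 1. Conditions in Section 12.1.1, side by side**

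| Category | Biochemistry and marrow | Baseline plasmacytoma | Lower category required? |
|---|---|---|---|
| sCR | Immunofixation negative, FLC ratio normal, marrow clear | None stated | No |
| CR | Immunofixation negative (or FLC ratio normal if no baseline M-spike), marrow clear | None stated | No |
| VGPR | Immunofixation only, or fall of at least 90% with urine below 100 mg/24 h | None stated | No |
| PR | Fall of at least 50%, plus urine limb | More than 50% reduction | No |
| MR | Fall above 25% and below 50% | None stated | No |
| SD | Change below 25% either way | None stated | No |

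Nesting cannot simply be assumed. Where the protocol builds one category on another it says so: in Section 12.2.1, CRu and PET-negative PR each refer back to the criteria for CR and PR.

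**Step 2. Test records.** Each has a baseline plasmacytoma with 0% change. The urine limb of PR is taken as met. M-protein stays visible on electrophoresis except in the last row. sCR is taken to count with CR in ORR.

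| M-protein result | Category as written | In ORR? |
|---|---|---|
| 30% fall | MR | No (in CBr) |
| 60% fall | None | No |
| 89% fall | None | No |
| 92% fall, urine below 100 mg/24 h | VGPR | Yes |
| Immunofixation negative, FLC ratio normal, marrow clear | CR and sCR | Yes |

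The 60% and 89% records show a second gap. They fail PR on the lesion, exceed the MR and SD ranges, and are not PD.

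**Step 3. Weight of one patient** = 1/n. The myeloma cohort is 8 in Section 14.0 and 15 in Section 9.3; Section 14.0 gives about 44 for the total at MTD.

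- n=8: 1/8 = 12.5 points (exact 95% CI for 1 of 8: 0.3% to 52.7%)
- n=15: 1/15 = 6.7 points (exact 95% CI for 1 of 15: 0.2% to 31.9%)
- n=44: 1/44 = 2.3 points

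**Step 4. How many patients.** The documents give no plasmacytoma prevalence. Every rate below is an assumption for illustration.

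- Carriers at 10–20%: 0.10 × 8 = 0.8 to 0.20 × 15 = 3, so about 1 to 3.
- Deep responders among carriers: 20–40%. Discordant lesion among those: 25–50%.
- Expected affected: 1 × 0.20 × 0.25 = 0.05 to 3 × 0.40 × 0.50 = 0.6.

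**Step 5. After the change.** With the lesion condition carried upward, the test patient meets none of sCR, CR, VGPR or PR at any M-protein fall. Without a further rule, the group with no category would then extend from falls of 50–89% to falls of 90% and above.

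**The case against.** The strongest reply is that Section 12.1.1 only summarises the IMWG criteria that Section 12.1 names as governing, and those may already deal with plasmacytomas in the higher categories. Footnote 8 orders PET/CT to confirm responses without limiting this to PR, so a CR with an unchanged mass could naturally be called unconfirmed. The central committee can also obtain the radiology.

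Much of this stands. A reader might infer that the trial will report complete responses in patients with visible tumour. The documents do not support that: the investigator, the confirmatory scan and the committee would all have to accept the response. A reader might also infer that every myeloma patient with a baseline plasmacytoma and a deep M-protein fall is affected. That is not so either, because where the lesion shrinks enough or disappears the category is the same under either wording.

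What does not stand is that the safeguards close the gap. The content of the cited criteria cannot be checked from these documents, and the tests listed in Section 12.1 include no lesion measurement. Footnote 8 names no result that the scan must show. The committee would be judging against the only definitions the protocol writes out.

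**Conclusion.** The gap in wording is real: as written, the same unchanged lesion blocks PR but not VGPR, CR or sCR. It bears only on patients with a deep M-protein fall whose plasmacytoma does not shrink by more than 50%. Their number is unknown and, on the assumed rates above, probably zero or one. If one occurs, the shift in the myeloma ORR is 12.5 or 6.7 points depending on which cohort size holds, against a confidence interval far wider than that. In the pooled analysis it is about 2.3 points.

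No decision in the trial turns on it. Sections 1.0 and 2.0 make MTD and safety primary; the passing statement in Section 16.1.2 that efficacy is a primary objective does not match them. Section 14.0 plans only proportions with confidence intervals for response, and there is no myeloma response threshold or stopping rule. The change is worth making because the rule gives an incoherent ordering and needs only a few words, not because the trial's conclusions are at risk.

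**What to change.** In Section 12.1.1:

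1. State that, if plasmacytomas were present at baseline, VGPR, CR and sCR also require at least the reduction required for PR.
2. State that CR and sCR require no residual plasmacytoma on the PET/CT of footnote 8. Check this against the cited IMWG criteria first. It parallels the protocol's own lymphoma CR, which allows no clinical, radiographic or diagnostic evidence of disease.
3. State that a patient who meets the M-protein limb of PR or better, fails the lesion condition and does not have PD is a non-responder for ORR, and assign a named category, for example SD. The SD range must be widened to fit. Say also how this sits with MR, which has no lesion condition: otherwise an unchanged lesion with a 30% fall counts in CBr while one with a 60% fall does not.

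Add the screening PET/CT for patients with plasmacytomas to Section 8.1, which names PET/CT or CT only for lymphoma, so that it agrees with footnote 8.

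The cost is a few clauses and no new procedure, since the scan is already ordered. CR, VGPR and ORR counts may fall slightly.

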## **12.0 CRITERIA FOR THERAPEUTIC RESPONSE/OUTCOME ASSESSMENT**

### **12.1 Multiple Myeloma:**

Responses will be determined according to the IMWG Response Criteria (that have supplanted the older European Group for Blood and Marrow Transplantation (EBMT) criteria) using standard electrophoretic and immunofixation tests of serum and urine for a monoclonal protein (M protein), the serum free light chain assay, and the bone marrow aspirate and biopsy with immunohistochemical staining. [Rajkumar SV, 2011]

For all patients responses will be assessed at the end of each cycle. Patients will have response of the myeloma assessed with serum and urine protein electrophoresis (SPEP/UPEP), serum and urine immunofixation (IF), quantitative immunoglobulins, and serum free light chain assay. A Patients will have a repeat bone marrow biopsy to confirm a biochemical complete response .

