### **12.1.2 Special Considerations in Assessing Response**

Low-level urinary M proteins may vary from measurement to measurement. For an increase in urinary M protein to be considered progression of disease it must be an absolute increase of at least  $200\text{ mg/day.}$

In quantitative immunoglobulin serum studies, the levels of heavy and light chain are often discrepant for technical reasons. If the discrepancy leads to equivocal response values, the heavy-chain value will be used since the heavy-chain value is usually a more reliable indicator because of its longer half-life and non-renal metabolism.

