## 3. Calculating Skin Scores

The sum of %TBSA by lesion is derived by summing the %TBSA from all regions affected by the lesion. The sum of %TBSA across lesion types (patches, plaques and tumors) within each region cannot exceed the %TBSA for the region. For example, the %TBSA for the head region is 7%. The sum of %TBSA across lesion types from head can only range from 0-7%. The skin score subtotal by lesion type are derived by multiplying the sum of %TBSA for patches from all regions by 1, sum of %TBSA of plaques from all regions by 2, and the sum of %TBSA of tumors or ulcers from all regions by 4. The skin score total is derived from summing the skin score subtotals for patches, plaques and tumors or ulcers. The skin score total is dimensionless with a scale of 0 to 400.

Region	% TBSA for the region	% TBSA Patch (or flat erythema)	% TBSA Plaque (or elevated/indurated erythema)	% TBSA Tumor/ Ulceration (or erythema w/fissuring, ulceration)
Head	7			
Neck	2			
Anterior Trunk	13			
Posterior Trunk	13			
Buttocks	5			
Genitalia	1			
Upper Arms	8			
Forearms	6			
Hands	5			
Thighs	19			
Lower Leg	14			
Feet	7			
% BSA by category	100			
Severity Weighting Factor		X 1	X 2	X 4
Skin Score Subtotal				

Responses will be determined by the criteria described in the table below. Progression of disease while on treatment should be confirmed by a second

assessment 1-4 weeks later so that patients who experience a temporary flare of disease due to skin infection or other intercurrent illnesses are not removed from the study prematurely.

Assessment	Description	Status
Completely clear	No evidence of disease; 100% improvement	CR
Marked Improvement	Greater than or equal to 50% decrease in skin scores compared	PR
Slight Improvement	Less than 50% decrease in skin scores compared to baseline	SD
Worse	
≥25% increase in skin scores compared to baseline while the patient is actively taking the study drug or ≥50% increase in the sum of the products of the greatest diameters of pathologically positive lymph nodes (should be documented by biopsy) compared to baseline while the patient is actively taking the study drug.
	PD

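### The protocol text calls myeloma progression on one reading above a running minimum, so at about 2 g/dL or more assay noise can shorten EFS

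*Combined protocol and SAP*

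**What the plan says.** Section 12.1.1 sets myeloma progression as "Increase of 25% from lowest response value in any of the following: serum M-component", the urine M-component or, only when serum and urine are not measurable, the FLC difference. The reference is the lowest value so far, not baseline. Each component also needs an absolute rise: 0.5 g/dL for serum ("serum M-component (minimal absolute increase of"), 200 mg/24h for urine, and 10 mg/dL for FLC ("the difference between involved and uninvolved FLC levels (absolute increase must be"). New hypercalcemia, lytic lesions or plasmacytomas also count.

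The Table 7 legend, footnote 11, sets the frequency: "Myeloma patients will have their disease assessed after each cycle". Section 12.1.2 recognises noise in one place, "Low-level urinary M proteins may vary from measurement to measurement", and answers it with the urine floor: "For an increase in urinary M protein to be considered progression of disease it must be an absolute increase of at least" 200 mg/day.

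Section 12.1 opens with "Responses will be determined according to the IMWG Response Criteria". Neither 12.1 nor 12.1.1 states a confirmatory reading for progression. For CTCL, Section 12.2.2 does: "Progression of disease while on treatment should be confirmed by a second" assessment 1 to 4 weeks later.

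Under Section 4.1, progression is an EFS event and ends DOR. Under 13.1 it is a reason to stop treatment. Section 14.0 pools the disease subtypes for these endpoints.

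**The concern.** The lowest of several noisy readings lies below the true level, and it can only fall as readings accumulate. A single later reading on the high side can then meet the 25% criterion although nothing has changed, and each further cycle is another chance for this. The error runs one way: it brings EFS events forward and can cut DOR short.

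An illustration under the written rule: readings of 3.0, 2.6 and 3.3 g/dL. Against the lowest, 3.3/2.6 = 1.27 and 3.3 − 2.6 = 0.7 g/dL, so both conditions for progression are met. Against baseline, 3.3/3.0 = 1.10, a rise that 12.1.1 would otherwise class as stable disease.

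**Working it through.** The plan states no false-progression rate and no assay CV, so there is no figure to reproduce. The CV below is an assumption and is shown as a range.

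**1. Where the floors stop binding.** A 25% rise equals the floor when the lowest value is floor/0.25:
- serum 0.5/0.25 = 2.0 g/dL
- urine 200/0.25 = 800 mg/24h
- FLC difference 10/0.25 = 40 mg/dL

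Below these values the floor asks for more than 25%. At 1 g/dL it asks for 0.5/1 = 50%; at 1.5 g/dL, 0.5/1.5 = 33%; at urine 300 mg/24h, 200/300 = 67%. Phase IIa eligibility (Section 6.1) starts at 0.5 g/dL serum or 200 mg/24h urine, so both protected and unprotected patients can enrol.

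**2. Simulation of a truly stable patient.** Inputs: constant true level; independent normal errors; one baseline plus 6 or 12 end-of-cycle readings; 200,000 patients per setting. Progression is called when a reading is at least 1.25 times the lowest earlier reading and the rise reaches the floor.

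False progression by cycle 6 / cycle 12:

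| True level | CV 5% | CV 7% | CV 10% |
|---|---|---|---|
| Serum 1 g/dL | 0% / 0% | 0% / 0% | 0.4% / 1.3% |
| Serum 2 g/dL | 0.4% / 1.3% | 9% / 24% | 40% / 73% |
| Serum 3 g/dL | 1.6% / 5% | 17% / 40% | 52% / 85% |

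At 0.5 g/dL the result is 0% by cycle 6 throughout. At 1.5 g/dL it is 0%, 0.7% and 13% by cycle 6. For urine at CV 15%, 300 mg/24h gives 1.5% by cycle 6, while 1,000 mg/24h gives 82% / 99%. With lognormal errors the result hardly changes: at CV 10%, 39% / 73% at 2 g/dL and 51% / 84% at 3 g/dL.

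**3. Responders.** A serum partial response requires a fall of at least half, so the level after response decides which row applies, counting cycles from the first reading at that level. At CV 10% over six further readings, a fall from 2 to 1 g/dL gives about 0.4% and a fall from 4 to 2 g/dL about 40%.

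**4. Scale in patients.** Section 14.0 plans 8 myeloma patients and Section 9.3 plans 15. If all were flat at 3 g/dL with CV 7%, expected false events by cycle 6 would be 8 × 0.17 = 1.4 or 15 × 0.17 = 2.6. If all were at 1 g/dL with CV 10%, they would be 8 × 0.004 = 0.03 or 15 × 0.004 = 0.06.

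**5. Two consecutive qualifying readings.** With both readings inside the window and both compared with the same earlier minimum, false progression by cycle 6 / 12 at 3 g/dL becomes 0.1% / 0.4% (CV 5%), 2.8% / 9% (CV 7%) and 16.5% / 43% (CV 10%). For urine 1,000 mg/24h at CV 15% it becomes 42% / 79%.

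**The case against.** Several stronger readings are tempting, and the documents do not support them.

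- **That no confirmation can apply.** Section 12.1 adopts the IMWG criteria by citation, and whether the cited source has a repeat rule cannot be checked from the documents. What can be said is that 12.1.1 writes out the operative criteria without one, so a reader working from it would not apply one.
- **That noise ends EFS in stable patients generally.** The floors nearly remove the problem at about 1 g/dL serum or 300 mg/24h urine and below, and at CV 5% it stays under 2% by cycle 6 even at 3 g/dL. The cycle 12 figures also presume twelve cycles of flat disease on treatment.
- **That DOR suffers equally.** Response halves the serum level or more, which moves many responders into the protected range. The effect remains mainly where the nadir stays near 2 g/dL or above.
- **That the CTCL rule shows myeloma was singled out.** The stated reason for the CTCL repeat is temporary flare from infection or other illness, not assay noise, and extracutaneous lymphoma (12.2.1) has no repeat either. The contrast shows only that the protocol accepts confirmation in principle.

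The impact is also limited. EFS and DOR are secondary, have no comparator, and serve a preliminary efficacy assessment. Section 16.1.2 makes responses subject to central review, but that is not a second sample. What stands is that the written rule can produce one-directional false events in patients with higher M-protein, and that samples already planned could reduce them.

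**Conclusion.** The concern holds in limited form. As written, 12.1.1 allows one reading above a running minimum to count as myeloma progression. For stable patients at about 2 g/dL or above, false progression by cycle 6 ranges from 0.4% to 52% across assumed CVs of 5% to 10%; at 1 g/dL it is at most 0.4%. The consequence is a downward bias in EFS for 8 or 15 myeloma patients and, diluted, in the pooled curve, with a smaller effect on DOR. The primary safety objective is not touched.

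The size depends on the assumed CV, on independent errors (laboratory drift would change the figures) and on the M-protein levels of the patients enrolled, which the documents do not give. This is a cheap improvement to a secondary endpoint, not a flaw that undermines the trial.

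**What to change.** In 12.1.1, for endpoint classification only, where progression rests on serum M-protein, urine M-protein or FLC alone:

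- require the 25% rise and the absolute increase on two consecutive readings; the second may be the next scheduled sample, an early repeat or the off-study sample;
- date progression at the first of the two;
- if no second reading is obtained, count progression at the first;
- require no repeat for progression by new lesions, plasmacytoma or hypercalcemia.

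State whether this matches the cited IMWG criteria. The sponsor should also reconcile it with 13.1, because progression is listed there as a reason to stop treatment and the second sample may otherwise not be taken. How treatment is handled in the meantime is for the sponsor to settle.

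**Cost.** A short addition to the text, plus that reconciliation. Sampling every cycle already supplies the second reading for patients who stay on study; others need an early repeat or an off-study sample. The progression call waits for one sample, but its date does not move. The rule lowers false progression without removing it (16.5% by cycle 6 remains at 3 g/dL and CV 10%), and an unrepeated reading still counts, so the gain depends on the second sample being obtained.

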- Grade 4 hematologic toxicities (attributed to study drugs) defined as:
  - Grade 4 thrombocytopenia (platelets  $< 25$  K/ $\mu$ L)
  - Grade 4 neutropenia (absolute neutrophil count (ANC)  $< 0.5$ )
- Grade 3 thrombocytopenia or neutropenia that results in a  $> 4$  day delay in any romidepsin dose in cycle 1.
- One week or greater delay in initiating cycle 2 day 1 due to continued drug-related toxicity.

At the time of enrollment the patients will be identified as representing three cohorts based upon disease subtype: 1) B-cell lymphoma 2) multiple myeloma 3) PTCL. Each disease specific cohort will enroll 15 patients. We plan to accrue 38 patients into the phase IIa portion including those treated at the MTD of the phase Ib portion. The assessment of toxicity and efficacy will be performed within the entire cohort evaluable at MTD. A preplanned exploratory analysis of the toxicity and efficacy of the disease specific cohorts will also be performed. Efficacy measures which will be determined include ORR, CBr (for myeloma), TTR, DOR, and EFS. ORR is defined as the percentage of patients achieving a best response of CR/CRu, very good partial response (VGPR--myeloma only), or PR at any disease assessment time point. CBr is defined as CR, VGPR, PR or MR (minimal response) in myeloma patients. TTR is defined as the time or number of cycles between study registration and documentation of first response (CR/Cru, VGPR, or PR). DOR is defined as the time or number of cycles between documentation of first response and progression, change of therapy, death, or date of last contact (if still alive without progression). EFS is defined as the time between study registration and documented progression, change in therapy, or death if no progression was observed.

[figure not shown]

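### Myeloma PR requires known plasmacytomas to shrink, but PD as written counts only new ones, so growth of an existing lesion alone is classed as SD, MR or continued response

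*Combined protocol and SAP*

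**What the plan says.** Section 12.1 opens the myeloma criteria with "Responses will be determined according to the IMWG Response Criteria". Section 12.1.1 then writes out each category.

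- **PR.** Besides the M-protein or light-chain fall, if plasmacytomas were present at baseline a more than 50% "reduction in the size of soft tissue plasmacytomas is also required".
- **PD, biochemical.** "Increase of 25% from lowest response value in any of the following: serum M-component", or urine M-component, each with an absolute minimum. The free light chain difference counts "only in patients without measurable serum and urine M-protein levels".
- **PD, other.** "new hypercalcemia, new lytic lesions by skeletal survey, or new soft tissue plasmacytomas".
- **SD.** The definition begins "Stable disease (SD) = An increase in the M protein by" and sets a bound of less than 25% from baseline in either direction. It has no plasmacytoma condition.
- **MR.** An M-protein reduction of more than 25% but less than 50%, again with no plasmacytoma condition. Under Section 4.1, "CBr is defined as CR, VGPR, PR or MR (minimal response) in myeloma patients".

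Section 12.1.2 adds notes on urinary M-protein and on discrepant immunoglobulin values, and nothing on plasmacytomas. Footnote 8 of the Table 7 legend says "PET/CT should be performed at screening and to confirm responses in patients with soft tissue plasmacytomas". Section 4.1 ends EFS at progression, change in therapy or death. It ends DOR at progression, change of therapy, death or last contact.

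**The concern.** The protocol treats a baseline plasmacytoma as measurable disease when it asks whether the patient has responded, and does not consider it when it asks whether the patient has progressed. Every imaging or clinical trigger in the myeloma PD definition is limited to something *new*, and a lesion recorded at screening cannot become new by growing.

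EFS and DOR are secondary endpoints, and Section 14.0 reports both pooled and by disease subtype. If assessors follow the written text, extramedullary growth may be dated late or recorded as another kind of event, and a patient whose lesion is growing can be counted as having clinical benefit. If some assessors follow the text and others apply a growth rule they take from the cited source, sites in this multicentre trial will classify the same scan differently.

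**Working it through.** The plan states no figure to reproduce. The check is to run three patients through the written definitions and then scale the effect of one reclassification. In each case no other PD trigger is met.

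**Classification under 12.1.1**

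1. *M-protein flat; a baseline plasmacytoma doubles.* The M-protein change is within 25%, so SD is met. There is no biochemical rise and no new lesion, so PD is not met. EFS runs on until another trigger, a change in therapy, or death. The patient is not a responder and contributes nothing to DOR.
2. *M-protein falls 30%; a baseline plasmacytoma grows.* A 30% fall lies between 25% and 50%, so MR is met and the patient counts in CBr. PD is not met.
3. *PR reached, with the required plasmacytoma shrinkage; the lesion then regrows while M-protein stays low.* The lesion is not new, so PD is not met and DOR continues.

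**Comparison within the protocol.** In Section 12.2.1, lymphoma PD includes an increase of at least 50% in the SPD of a previously identified node. In Section 12.2.2, CTCL PD includes an increase of at least 25% in the skin score. Both count growth of known disease. The myeloma definition counts rising biochemical markers but not growth of a known mass.

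**Scale of one reclassified patient.** The myeloma cohort is 8 in Section 14.0 and 15 in Section 9.3. The pooled set is about 44 in Section 14.0 (15 + 8 + 15 + 6 = 44).

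- Myeloma subset: 1/8 = 12.5 points; 1/15 = 6.7 points.
- Pooled set: 1/44 = 2.3 points.

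These are crude proportions. A Kaplan-Meier step equals 1/n only while nobody has left the risk set, and is larger later.

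**Number at risk.** The documents give no frequency of baseline plasmacytomas. If, as an assumption only, 10% to 20% of myeloma patients have one, the expected count runs from 0.10 × 8 = 0.8 to 0.20 × 15 = 3.0, or about 1 to 3 patients. These are patients who could be affected. Misclassified patients would be only those whose lesion grows while every other trigger stays negative.

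**The case against.** The strongest reply is that Section 12.1 makes IMWG the governing standard, so 12.1.1 may be only a summary and an assessor could apply a growth rule from the source. The source cannot be checked here, and the point does not rely on its content. What can be said is that 12.1.1 sets out full definitions, none covers growth of an existing plasmacytoma, and nothing says that the citation completes or overrides them. If a growth rule is intended, it is not in the text that sites will use.

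Three further replies narrow the point.

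- A reader might infer that such growth is never captured and that EFS and DOR are simply too long. The documents do not support that. Change of therapy ends both intervals, so growth that prompts a switch does produce an event, dated at the switch and not labelled progression. Another PD trigger may also fire: phase IIa myeloma patients must have a measurable serum, urine or light-chain marker (Section 6.1), and disease is assessed every cycle. DOR is affected only by regrowth in responders.
- A reader might infer that these patients must stay on treatment. Section 4.2 also ends treatment on the treating physician's recommendation. What is missing is the route through the progression rule.
- The myeloma analysis is an exploratory subset of secondary endpoints. The primary objective is MTD and safety, which this does not touch.

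All three stand as limits on the size of the effect. None removes the mismatch between the PR and PD clauses.

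**Conclusion.** The point holds as an inconsistency in the written endpoint definitions. Taken literally, isolated growth or regrowth of a known plasmacytoma is SD, MR or continued response. The consequence is late dating of the event, or labelling it as change of therapy, in EFS and, for responders only, in DOR. CBr can also count a patient whose extramedullary disease is growing. Certain omission of the event is not established.

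The number of patients affected is unknown. Each one is worth 6.7 to 12.5 points of the myeloma subset and about 2.3 points of the pooled set. The assumed 1 to 3 patients should be read as a number at risk and not as a count of missed events. The conclusion rests on reading 12.1.1 as the operative text. It would fall away if the sponsor showed that a growth rule is already in force at all sites under the IMWG reference, and in that case the rule should still be written down. The correction is worth making because it is cheap and the subset is small.

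**What to change.** Reconcile the PR and PD clauses of 12.1.1 with each other and with the IMWG reference in 12.1. A measured increase in an existing soft tissue plasmacytoma should count as progression for EFS and DOR, and should override SD and MR. Use the same measurement as for PR. The sponsor should take the threshold and the reference value (baseline or smallest recorded size) from its named criteria and state both. Because progression also appears in Section 13.1 as a reason to stop treatment, the text should say how the endpoint definition relates to that list. That is for the sponsor to decide.

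Apply the rule to examinations and scans that are done anyway, including the end-of-study assessments. The explicit instruction to image at discontinuation is in footnote 7, which covers lymphoma, so the sponsor should say whether it also applies to myeloma patients with plasmacytomas.

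The cost is a few lines of text, with no change to sample size. Some events will be dated earlier, so EFS and DOR may look somewhat shorter. The change does not fully solve detection. Footnote 8 calls for PET/CT only at screening and to confirm responses, so a non-palpable lesion in a patient with no response to confirm may grow between scans and still be dated late. Unless imaging is added, the plan should state that limitation.
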